2.2. Study Objective(s) and Endpoint(s)

Objectives	Endpoints
Primary Objectives	Primary Endpoints

 To demonstrate non-inferiority of GSK1278863 to epoetin beta pegol based on hemoglobin (Hgb) in ND subjects 	
 Mean Hgb during the primary efficacy evaluation period (Weeks 40 to 52)
Principal Secondary Objectives	Principal Secondary Endpoints

 To demonstrate superiority of GSK1278863 to epoetin beta pegol in terms of achievement/maintenance of target Hgb in ND subjects 	
 Number (%) of subjects with mean Hgb in the target range (11.0-13.0 g/dL) during the primary efficacy evaluation period (Weeks 40 to 52)
Other Secondary Objectives	Other Secondary Endpoints

 To evaluate the appropriateness of the starting dose of GSK1278863 in ND subjects using epoetin beta pegol as control To evaluate the appropriateness of the starting dose of GSK1278863 in PD subjects 	
 Change in Hgb from baseline to Week 4 (Hgb increase rate) Number (%) of subjects by Hgb change category in Hgb from baseline to Week 4

 To evaluate dose adjustments of GSK1278863 in ND subjects using epoetin beta pegol as control To evaluate dose adjustments of GSK1278863 in PD subjects 	
 Distribution of the dose level Duration of treatment interruption due to Hgb >13 g/dL Frequency of dose adjustments

 To evaluate the overall Hgb control by GSK1278863 in ND subjects using epoetin beta pegol as control To evaluate the overall Hgb control by GSK1278863 in PD subjects 	
 Hgb at each assessment time point and change in Hgb from baseline to each assessment time point Number (%) of subjects with Hgb within the target range (11.0-13.0 g/dL) at each assessment time point Proportion (%) of time with Hgb within the target range (11.0-13.0 g/dL) in the primary efficacy evaluation period (Weeks 40 to 52) Time (number of days) to the lower Hgb target (11.0 g/dL) Number (%) of subjects who have an Hgb level of less than 7.5 g/dL Number (%) of subjects who have an Hgb increase of more than 2 g/dL over any 4 weeks before Week 52 Number (%) of subjects who achieve an Hgb level of more than 13.0 g/dL and number of episodes

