A scatter plot of Hgb values measured by Central Laboratory versus Hgb values measured by Hemocue will be produced along with Pearson's correlation coefficient. Regardless of visit and treatment group, all available pairs of Hgb (i.e. non-missing values in both from central laboratory and from the corresponding HemoCue measurement) will be used.

- **Dose adjustment**

The dose adjustment algorithm is described in Section 15.6.3, based on HemoCue Hgb values.

Dose at each assessment visit / final visit

Dose at each assessment visit and final visit will be summarized by treatment group using mean, standard deviation, minimum, P25, median, P75, mode, and maximum at each assessment visit. The final visit will be the last visit of treatment exposure for each subject. Mean dose during Week 40 to 52 will also be summarized and includes subjects who has at least one exposure record during Week 40 to 52. The summary will also be provided by Prior ESA use, prior ESA dose, prior ESA type, and ERI.

Duration (days) of treatment interruption due to Hgb >13.0 g/dL

The number and percentage of subjects who have a period of treatment interruption due to Hgb >13.0 g/dL will be summarized by treatment group. On subjects who have a period of treatment interruption due to Hgb >13.0 g/dL, the duration (in days) of treatment interruption due to Hgb >13.0 g/dL per subject will be summarized by treatment group using mean, standard deviation, minimum, P25, median, P75, and maximum. On-therapy Hgb values observed in scheduled visits will be counted in the summary. The summary will also be provided by prior ESA use.

Dose adjustment

The number and percentage of subjects with dose adjustments will be provided. Number of dose adjustments will be summarized by treatment group using mean, standard deviation, minimum, median, mode, and maximum. For dose adjustments frequency, the number and percentage of subjects will be provided by the number of dose adjustments (i.e. zero, one, two, three, four, ..., ten, eleven, and twelve or more; may be refined) by treatment group during the whole treatment period. For timing of dose adjustments, the

number and percentage of subjects with dose adjustments by each assessment visit will be provided by treatment group. The summary will also be provided by Prior ESA use.

Dose adjustment to reach the lower Hgb target (11.0 g/dL)

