
 • Time to reach the lower Hgb target will be determined as follows: 
 ○ Time to reach the lower Hgb target = Date to reach the lower Hgb target – Randomization Date + 1 day • Subjects who could not reach the lower Hgb target during on-therapy will be regarded as censored. Censored time will be determined as follows: 
 ○ Censored time = Treatment Stop Date – Randomization Date + 1
Dose Adjustment
Dose adjustment algorithm

 • Dose Adjustment algorithm will be based on HemoCue Hgb values at scheduled visits. No Hgb values measured at unscheduled visits will be included. • Dose will be derived from actual dose. • The following table illustrates the algorithm using analysis flags as below: 
 ○ (FL_A): Adjustment flags will be counted if actual dose is changed from that of the previous visit.

Dose Adjustment

- (FL_B): Over 13 g/dL flags will be counted if HemoCue Hgb >13 g/dL is observed.
 - (FL_C): Interruption flags will be counted if actual dose is zero.
- Treatment durations in each visit will be calculated based on the following formula:
- Daprodustat
Duration (days) = Treatment Stop Date in the visit – Treatment Start Date in the visit + 1 day
 - Epoetin beta pegol group
Treatment stop date in the visit will be derived from [treatment start date in the next visit – 1 day]. If there is no record of the next scheduled visit, Treatment Stop Date (see Section 15.6.1) will be applied for the record.

Illustration of dose adjustment algorithm (24-week case)

Visit (Example)	Treatment Start date/ Stop date	Duration	HemoCue Hgb (g/dL)	Dose (mg)	(FL_A)	(FL_B)	(FL_C)
					Adjust-ment	Over 13 g/dL	Inter-ruption
Day 1	PPD	29	11.1	4	N	N	N
Week 4		14	11.4	4	N	N	N
Week 8		30	11.8	2	Y	N	N
Week 12		31	13.4	0	Y	Y	Y
Week 16		30	12.6	0	N	N	Y
Week 20		31	11.7	1	Y	N	N
Week 24	-	-	12.3	-	-	N	-

For programmers, note that the flags are for the purposed of illustration, and are not intended to imply any type of requirement.

- For summary tables, further details are described within the next items;
- 'Duration (days) of treatment interruption due to Hgb >13 g/dL'
 - 'Dose adjustment'
 - Number of dose adjustment to reach the lower Hgb target (11.0 g/dL)

Duration (days) of treatment interruption due to Hgb >13.0 g/dL

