Calculation of duration of treatment interruption due to Hgb >13.0 g/dL will be based on the dose adjustment algorithm specified in the protocol.

- Duration (days) = Sum of [Duration]_n
where
[Duration]_n represents exposure duration at visit n to meet the following.
 - Treatment interruption is made due to HemoCue Hgb over 13 g/dL and consecutive until treatment is resumed.

In the above illustration, duration = 61 (days), from Week 12 and 16 visit records.

Dose adjustment

Calculation of frequency of dose adjustment will be based on the above algorithm.

- Number of dose adjustment will be counted for each subject as follows:
 - Counts of adjustment flag = 'Y'

Dose Adjustment
Number of dose adjustment to reach the lower Hgb target (11.0 g/dL)

 Reaching the lower Hgb target will be determined on the basis of central laboratory Hgb. Subjects who has a baseline central laboratory Hgb value within target range or who does not reach the lower Hgb target during treatment period will be excluded from the summary. Number of dose adjustment to reach the lower Hgb target will be counted for each subject as follows 
 Counts of adjustment flag = 'Y' at visits before Date to reach the lower Hgb target.

Iron Endpoints									
Oral Iron Use									

 The following iron-containing drugs will not be included in the analysis of iron use. 
 GSK drug code: 54909401 (SUCROFERRIC OXYHYDROXIDE; P-TOL). 									
Subjects who used IV and/or oral iron									

 Number of subjects who used IV and/or oral iron will be summarized Subjects who used IV and/or oral iron will be defined as follows: 
 Subjects with on-therapy IV and/or oral iron medication collected in a specific eCRF form (CONMEDS-IRON). Regarding oral iron use, the number of subjects who used ferric citrate and other than ferric citrate will also be counted respectively. 									
Oral Iron Dose by Quarter									

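### Frequency of dose adjustments is reported as a raw count per subject over unequal follow-up, so it mixes how often doses changed with how long subjects stayed

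*SAP*

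**What the plan says.** SAP 2.2 lists "Frequency of dose adjustments" among the other secondary endpoints, under an objective that is comparative for non-dialysis subjects: "To evaluate dose adjustments of GSK1278863 in ND subjects using epoetin beta pegol as control".

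Section 7.3.2 gives the summary: "Number of dose adjustments will be summarized by treatment group", with the mean, SD, minimum, median, mode and maximum. It adds a distribution by category, "zero, one, two, three, four, ..., ten, eleven, and twelve or more; may be refined) by treatment group during the whole treatment period", and the number and percentage of subjects adjusted at each visit. No denominator is stated for the by-visit percentages.

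Section 15.6.3 derives the number. "Adjustment flags will be counted if actual dose is changed from that of the previous visit", and the subject's total is the sum of those flags ("Number of dose adjustment will be counted for each subject as follows").

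The displays are Tables 2.66 and 2.68 (ITT) and 2.67 and 2.69 (Efficacy PD). Section 4 admits a subject to either population with a baseline Hgb and one later scheduled Hgb. Section 7.3.4 treats intercurrent events as irrelevant for secondary endpoints and uses observed data. Section 15.7.1 keeps the available data of withdrawn subjects in the tables.

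**The concern.** A flag needs a dose record that differs from the one before it, so none can arise after a subject stops. The count is therefore bounded by the number of dosing visits attended, and that number differs between subjects. None of the sections above divides by time or by dosing visits, sets a common window, or separates early leavers.

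Elsewhere the plan does allow for duration. Oral iron is a monthly average (15.6.3), study drug is a daily or monthly average over time on treatment (15.6.2), time in range is also a percentage of the period (15.6.3), and time to the lower Hgb target is censored (15.6.3). The adjustment count has no counterpart to these.

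At stake is the reading of four descriptive tables. In the ITT tables, unequal withdrawal would produce a difference in mean count, and in the share with no adjustments, even if doses were changed equally often while subjects were treated. In the single-arm PD tables there is no contrast to tilt, but the distribution still blends retention with adjustment.

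**Working it through.** **The plan's own illustration.** The SAP gives no target figure for this endpoint, so the check starts from the 24-week example in 15.6.3. Doses at Day 1 and Weeks 4, 8, 12, 16 and 20 are 4, 4, 2, 0, 0 and 1 mg. The flag rule marks Weeks 8, 12 and 20, a count of 3, which matches the printed flags. The interruption of 31 + 30 = 61 days also matches. The same subject would count 0 if last dosed at Week 4, 1 if last dosed at Week 8, and 2 if last dosed at Week 12 or 16.

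**Inputs for the size.**
- Decisions for a completer: Weeks 4 to 48 in four-week steps, K = 12 (dose changes every 4 weeks, SAP 2.3).
- Adjustment probability per decision, p: not in the SAP. Assumed 0.20 to 0.40, equal in both arms.
- Withdrawn fraction, w: not in the SAP. Assumed 5% to 30%.
- Timing: a withdrawn subject is assumed equally likely to have had 0, 1, ..., 11 decisions, a mean of 5.5.

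**Mean count** = p × [12(1 − w) + 5.5w].

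| w | mean decisions | mean count, p = 0.20 | p = 0.30 | p = 0.35 | p = 0.40 |
|---|---|---|---|---|---|
| 0% | 12.00 | 2.40 | 3.60 | 4.20 | 4.80 |
| 10% | 11.35 | 2.27 | 3.41 | 3.97 | 4.54 |
| 20% | 10.70 | 2.14 | 3.21 | 3.75 | 4.28 |
| 30% | 10.05 | 2.01 | 3.02 | 3.52 | 4.02 |

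The ratio between arms does not depend on p. For 10% versus 20% withdrawal it is 10.70/11.35 = 0.943, a gap of 5.7%. For 10% versus 30% it is 10.05/11.35 = 0.885, a gap of 11.5%. Conversely, the arm with more withdrawal could have a per-decision probability higher by 11.35/10.70 − 1 = 6% or 11.35/10.05 − 1 = 13% and still show the same mean.

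**Share with zero adjustments** = (1 − w)(1 − p)^12 + w × A, where A = [1 − (1 − p)^12]/(12p) is the mean of (1 − p)^k over k = 0 to 11. The second term is the part contributed by withdrawals.

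- p = 0.20: (0.80)^12 = 0.0687 and A = 0.9313/2.4 = 0.388. At w = 10%: 0.0618 + 0.0388 = 10.1%, of which 39% are withdrawals. At w = 20%: 0.0550 + 0.0776 = 13.3%, of which 59%. At w = 5% the withdrawal share is 23%.
- p = 0.35: (0.65)^12 = 0.0057 and A = 0.9943/4.2 = 0.237. At w = 10%: 0.0051 + 0.0237 = 2.9%, of which 82% are withdrawals. At w = 20%: 0.0046 + 0.0473 = 5.2%, of which 91%.

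**Sensitivity to the constant-probability assumption.** If p varies between subjects as a beta distribution with mean 0.35 and a + b = 4, the withdrawal shares of the zero category fall to 27% (w = 10%) and 46% (w = 20%). If adjustments come early (0.6 at the first four decisions, 0.225 at the next eight, total still 4.2), the mean counts are 4.02 and 3.85 at 10% and 20% withdrawal, a gap of 4.4% instead of 5.7%.

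**After dividing by decisions.** With equal constant p, total adjustments over total decisions equals p in both arms at any withdrawal level, for example 0.30 and 0.30.

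**The case against.** The strongest reply is that this is a description, not a test. Section 7.3.1 marks dose adjustment under summary displays only, and 7.3.2 plans no difference or confidence interval for it, unlike time in range and oral iron. Section 5.5 says other secondary endpoints are compared at the two-sided 5% level, but no comparison is specified for this one. This stands, and it limits the weight of the point.

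Unequal follow-up is also visible elsewhere: withdrawal and discontinuation in Tables 1.1 and 1.3, time on treatment in Table 1.55, adjustments by visit within 7.3.2, and dose by visit with a category for not available (Tables 2.74 and 2.75). This stands in part. Exposure is summarised on the Safety population, the by-visit denominator is unstated, and none of these displays changes the count or the category table. The table shells are in a separate document that is not shown.

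Two stronger readings are tempting, and the document supports neither. A reader might infer that the arm with more dropout will look better titrated. The SAP never says that fewer adjustments are better, and it gives no withdrawal rates. With equal adjustment behaviour, and withdrawal equal in amount and timing, the contrast is not tilted. A reader might also infer that the zero category will consist mainly of leavers. That depends on the assumptions: it holds at p = 0.35 with constant probability, but fails at p = 0.20 with 5% or 10% withdrawal, and fails at mean 0.35 under the between-subject variation assumed above.

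**Conclusion.** The point holds as a defect of a descriptive secondary display. As specified, the mean count and the category distribution mix adjustment frequency with retention. The arm contrast is tilted to the extent that withdrawal differs. With 12 decisions, equal probability in both arms and evenly spread withdrawal, the tilt is about 5.7% of the mean count for 10% versus 20% withdrawal (0.23 adjustments over the year at p = 0.35). It is smaller if adjustments come early. At 10% withdrawal, leavers make up about 39% (p = 0.20) to 82% (p = 0.35) of the zero category under constant probability. These sizes are illustrations over assumed ranges, not predictions for this trial. The primary and principal secondary analyses do not use the count and are unaffected.

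**What to change.** In 7.3.2 and 15.6.3 (Tables 2.66 to 2.69):

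- Keep the raw count and its distribution.
- Add, by arm, total adjustments divided by the total scheduled four-weekly dosing visits, from Week 4 onward, at which subjects had a dose record. Counting visits rather than days avoids relying on the assumed epoetin beta pegol stop date in 15.6.1.
- Report any Week 2 change separately, because SAP 2.3 describes a Week 2 change only for daprodustat in Cohort 3. Pooling it would give the arms different numbers of opportunities.
- Show the number of dosing visits, or time on treatment, in the same table.
- State that the denominator of the by-visit percentages is subjects with a dose record at that visit.

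Do not scale individual subjects to 52 weeks: one adjustment in a single decision would become 12, and early leavers would turn into extreme values. A distribution restricted to subjects with a Week 48 dosing record selects on a post-randomisation event, so it should appear only as a labelled supplementary display.

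The cost is a short wording change and a few rows in existing tables. No new data are needed.

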
 To compare the effect of GSK1278863 versus epoetin beta pegol on iron use in ND subjects To evaluate effect of GSK1278863 on iron use in PD subjects 	
 Dose of oral iron in the study period and the primary efficacy evaluation period (Weeks 40 to 52) Number (%) of subjects who use oral iron during the primary efficacy evaluation period (Weeks 40 to 52)

 To compare the effect of GSK1278863 versus epoetin beta pegol on iron metabolism in ND subjects To evaluate the effect of GSK1278863 on iron metabolism in PD subjects 	
 Change in ferritin from baseline Change in transferrin saturation (TSAT) from baseline Changes in hepcidin, serum iron, and total iron binding capacity (TIBC) from baseline

Objectives	Endpoints

 To evaluate the PK of GSK1278863 	
 AUC and Cmax of plasma GSK1278863
Exploratory Objectives	Exploratory Endpoints

 To compare the effect of GSK1278863 versus epoetin beta pegol on progression of CKD in ND subjects 	
 Estimated glomerular filtration rate (eGFR) and change from baseline Serum creatinine and change from baseline Urine creatinine and urine albumin, and changes from baseline Urine albumin/creatinine ratio and change from baseline
Patient Reported Outcome	Patient Reported Outcome Endpoints

 To compare the effect of GSK1278863 versus epoetin beta pegol on health-related QoL (HR-QoL) in ND subjects To evaluate the effect of GSK1278863 on HR-QoL in PD subjects 	
SF-36
 
 Changes in SF-36 HR-QoL scores (PCS, MCS, and 8 subscales) from baseline 
EuroQol Health Utility Index (EQ-5D-5L)
 
 Change in EQ-5D-5L score from baseline Change in EQ-5D-5L Visual Analog Scale (VAS) from baseline
Safety Objectives	Safety Endpoints

 To evaluate the safety and tolerability of GSK1278863 in ND and PD subjects 	
 Incidence and severity of AEs and SAEs, including AEs of special interest Reasons for discontinuation of study medication Laboratory tests, ECG, vital signs, and ophthalmology assessments

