Number of dose adjustment to reach the lower Hgb target (11.0 g/dL) by prior ESA use			Y			
Number (%) of subjects with each dose at each assessment visit			Y	Y		
Number(%) of subjects with each dose at each assessment visit by prior ESA ^[1]			Y	Y		
Hgb and Dose						
Profiles of Hgb and dose over time					Y	
Iron Use						
Dose of oral iron (mg) during the treatment period and the primary efficacy evaluation period (Week 40 to 52)			Y			
Change from baseline in dose of oral iron (mg) during the treatment period and the primary efficacy evaluation period			Y			
Dose of oral iron (mg) during the treatment period and the primary efficacy evaluation period (Week 40 to 52) by Baseline Iron Use			Y			
Number (%) of subjects who use iron during the treatment period and the primary efficacy evaluation period (Week 40 to 52)			Y			
Number (%) of subjects who use iron during the treatment period and the primary efficacy evaluation period (Week 40 to 52) by Baseline Iron Use			Y			

[Endpoint / Parameter/ Display Type]	Absolute					
	Stats Analysis		Summary		Individual	
	T	F	T	F	F	L
Iron Parameters (ferritin, TSAT, hepcidin, serum iron, TIBC)						
Raw observed value at each assessment visit			Y	Y		Y
Raw observed value at each assessment visit by Subgroup ^[7]			Y	Y		
Change from baseline at each assessment visit	Y	Y	Y			
Change from baseline at each assessment visit by Subgroup ^[7]	Y	Y ^[8]	Y			

NOTES :

- T = Table, F = Figure, L = Listing, Y = Yes display generated.
- Stats Analysis = Represents TFL related to any formal statistical analyses (i.e. modelling) conducted.
- Summary = Represents TFL related to any summaries (i.e. descriptive statistics) of the observed raw data.
- Individual = Represents FL related to any displays of individual subject observed raw data.

[1] prior ESA use, prior ESA dose, prior ESA type, and ERI

[2] <=-1, >-1 to -0.5, >-0.5 to 0, >0 to 0.5, >0.5 to 1, >1 g/dL, within ± 0.5 g/dL and over ± 1 g/dL for Week 2

<=-2, >-2 to -1, >-1 to 0, >0 to 1, >1 to 2, >2 g/dL, within ± 1 g/dL and over ± 2 g/dL for Week 4

[3] Not only within the target range, but also with above and below target range will be assessed.

[4] Rosendaal method will be used (See Section 15.6.3).

[5] Kaplan-Meier method will be used to estimate P25, median and P75. Subjects within target range at baseline and subjects who could not reach lower target will be regarded as censored.

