Change from baseline in average oral iron dose (See Section 15.6.3) will be summarized using mean, standard deviation, minimum, P25, median, P75, and maximum. Quarter 1 (Day 1 to Week 12), Quarter 2 (Week 12 to Week 24), Quarter 3 (Week 24 to Week 40), Quarter 4 (Week 40 to Week 52), and whole treatment period will be used and Quarter 4 represents the primary efficacy evaluation period. For the ITT population, the treatment differences (daprodustat – epoetin beta pegol) and the associated 95% CIs will also be provided.

Number (%) of subjects who use iron during the treatment period and the primary efficacy evaluation period

The number and percentage of subjects who use iron during the screening period as baseline, the treatment period, and the primary efficacy evaluation period will be summarized separately. These will be also summarized by baseline iron use defined in Section 5.4.2

- **Iron Parameter (ferritin, TSAT, hepcidin, serum iron, and TIBC)**

Based on literature review the distributions of TSAT and hepcidin are skewed and require a log-transformation (See Section 5.2).

Raw observed value at each assessment visits

Ferritin, serum iron, and TIBC values will be summarized by treatment group using mean, standard deviation, 95% CI, minimum, P25, median, P75, and maximum at each assessment visit. TSAT and hepcidin values will be summarized by treatment group using geometric mean, standard error, coefficient of variation, and 95% CI based on log-transformed parameters, median, minimum, and maximum based on original scale at each assessment visit. Graphical summaries will also be provided for each iron parameter. These will be also summarized by baseline iron use, prior ESA use.

Change from baseline at each assessment visit

Change from baseline in ferritin, serum iron, and TIBC values will be summarized by treatment group using mean, standard deviation, 95% CI, minimum, P25, median, P75, and maximum at each assessment visit. Percent Change from baseline in TSAT and hepcidin values (Section 5.2) will be summarized by treatment group using geometric mean, coefficient of variation, and 95% CI based on log-transformed parameters, minimum, median, and maximum based on original scale at each assessment visit.

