7.3.5. Statistical Analyses / Methods

Details of the planned displays are provided in [Appendix 10](#): List of Data Displays and will be based on GSK data standards and statistical principles.

Unless otherwise specified, endpoints / variables defined in Section 7.3.1 will be summarized using descriptive statistics, graphically presented (where appropriate) and listed.

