7.3.5.1. Statistical Methodology Specification

Endpoint / Variables

 Change from baseline in the respective iron parameter at each assessment visit
Model Specification

 Analyses will be repeated for each iron parameter (ferritin/TSAT/hepcidin/serum iron/TIBC) using MMRM as follows: $\text{Iron}_{ik} = \beta_0 + \beta_{\text{baseline}} * \text{Baseline}_i + \beta_j + \beta_k + \beta_{jk} + \beta_{\text{baseline}*k} * \text{Baseline}_i + \epsilon_{ik}$ 
Iron_{i, week}: change from baseline in iron measurement for subject i at visit k

β_0 : Intercept
 β_{baseline} : baseline effect of each iron parameter
 Baseline_i: the baseline value of each iron parameter for subject i
 β_j : treatment effect (j= daprodustat, epoetin beta pegol)
 β_k : visit effect (k = Week 4, Week 16, Week 28, Week 40, Week 52)
 β_{jk} : treatment-by-visit interaction
 $\beta_{\text{baseline}*k}$: baseline-by-visit interaction
 ϵ_{ik} : random error for subject i at visit k
 i: subject (i = PPD ..., N)
 N: number of subjects included in the analysis

- The model parameters will be estimated using Restricted Maximum Likelihood (method=REML) with the Newton-Raphson algorithm.
- The Kenward-Roger method for calculating the denominator degrees of freedom will be used.
- The variance-covariance structures for repeated measures within the individual subject will be unstructured (type=UN).
- LS mean change from baseline for treatment j at visit k will be calculated as follows for each iron parameter.

$$\mu_{jk} = \beta_0 + \beta_{\text{baseline}} * \mu_{\text{baseline}} + \beta_j + \beta_k + \beta_{jk} + \beta_{\text{baseline}*k} * \mu_{\text{baseline}}$$

μ_{jk} : LS mean change from baseline for treatment j at visit k
 μ_{baseline} : mean for the baseline value of each iron parameter

- The treatment difference at visit k for model based mean change from baseline will be calculated as follows for each iron parameter as adjusted treatment difference

$$\mu_{\text{daprodustat}*k} - \mu_{\text{epoetin beta pegol}*k} = \beta_{\text{daprodustat}} - \beta_{\text{epoetin beta pegol}} + \beta_{\text{daprodustat}*k} - \beta_{\text{epoetin beta pegol}*k}$$

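### SAP Section 7.3.2 names no model for the treatment difference in oral iron dose; adjusting for the baseline dose already derived would sharpen the estimate at no cost

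*SAP*

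**What the plan says.** Section 2.2 lists the objective "To compare the effect of GSK1278863 versus epoetin beta pegol on iron use in ND subjects", with oral iron dose over the study and over Weeks 40 to 52 as an endpoint. The only between-arm estimate for that dose is in Section 7.3.2, which begins with description: "Change from baseline in average oral iron dose (See Section 15.6.3) will be summarized using mean, standard deviation, minimum, P25, median, P75, and maximum". After these descriptive statistics, for each quarter and the whole treatment period, it adds: "For the ITT population, the treatment differences (daprodustat – epoetin beta pegol) and the associated 95% CIs will also be provided". The only cross-reference for this variable is to Section 15.6.3, whose iron derivations define doses and periods but name no model or covariate.

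Four other places bear on the method:

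- Section 7.3.5 sets the default: "Unless otherwise specified, endpoints / variables defined in Section 7.3.1 will be summarized using descriptive statistics, graphically presented (where appropriate) and listed".
- Section 7.3.5.1 limits the modelling: "Analyses will be repeated for each iron parameter (ferritin/TSAT/hepcidin/serum iron/TIBC) using MMRM as follows". Oral iron dose is not in that list.
- Section 7.3.1 marks the display "Change from baseline in dose of oral iron (mg) during the treatment period and the primary efficacy evaluation period" under Summary and not under Stats Analysis. Table 2.82 in Section 15.10.4.2 is likewise titled a summary.
- Section 15.6.3 defines a baseline period from screening to the day before randomization and sets non-users to 0 mg in all-subject summaries, so a baseline dose is available.

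**The concern.** The laboratory iron parameters get a baseline-adjusted difference (Section 7.3.5.1), and so do the quality-of-life changes (Sections 9.2 and 9.5.1). Oral iron dose, which serves a stated comparison objective, appears to get a plain difference of change scores although its baseline is derived.

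Subtracting the baseline forces its coefficient to 1. Where the true slope of on-treatment dose on screening dose differs from 1, the change score carries avoidable variance and handles chance baseline imbalance imperfectly. Randomization is stratified by ESA use and hemoglobin (Section 5.4.1), so iron dose is not balanced by design. What is at stake is the width of one set of confidence intervals, and a method left to inference.

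**Working it through.** **Inputs from the SAP.** Two-sided 5% without multiplicity adjustment for other secondary endpoints (Section 5.5); 1:1 allocation and about 286 non-dialysis subjects (Section 2.3), so 286/2 = 143 per arm for illustration. The ITT set with Quarter 4 data will be smaller, but the relative widths below do not depend on N.

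**Inputs the SAP does not give.** SDs, the baseline-to-treatment correlation ρ, a target effect and power for oral iron dose. These are assumed and shown over a range. There is no SAP figure to reproduce.

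**Step 1: general comparison.** Let s0 and s1 be the SDs of baseline and on-treatment dose. With the same allocation factor for both methods:

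- change score: variance ∝ s0² + s1² − 2ρ·s0·s1
- ANCOVA: variance ∝ s1²(1 − ρ²)
- gap: s0² − 2ρ·s0·s1 + ρ²·s1² = (s0 − ρ·s1)² ≥ 0

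The gap is zero only if ρ·s1/s0 = 1, that is, if the slope on baseline is 1. Apart from one degree of freedom, ANCOVA is never less precise.

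**Step 2: equal SDs.** The variance ratio, adjusted to change, is (1 − ρ²)/[2(1 − ρ)] = (1 + ρ)/2, so the CI width ratio is √((1 + ρ)/2). The half-width in SD units is 1.96·√(2/143) = 0.232, multiplied by √(2(1 − ρ)) for the change score and by √(1 − ρ²) for ANCOVA. For power, take an effect that the change-score analysis detects with 80%: adjusted power = Φ[(1.96 + 0.8416)/√((1 + ρ)/2) − 1.96].

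| ρ | Half-width, change | Half-width, adjusted | Adjusted CI narrower by | Adjusted power (from 80%) |
|---|---|---|---|---|
| 0.3 | 0.274 | 0.221 | 19% | 93.5% |
| 0.5 | 0.232 | 0.201 | 13% | 89.9% |
| 0.7 | 0.180 | 0.166 | 8% | 86.0% |
| 0.9 | 0.104 | 0.101 | 2.5% | 82.0% |

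At ρ = 0.75: 2.8016/√0.875 − 1.96 = 1.035, and Φ(1.035) = 85.0%. The gain is therefore under 5 points from about ρ = 0.75 upward. Below ρ = 0.5 the change score is less precise even than comparing on-treatment dose with no baseline at all (half-width 0.232).

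**Step 3: unequal SDs.** With s1/s0 from 0.75 to 1.5 and ρ from 0.3 to 0.9, the change-score CI is wider by between 0.1% (s1/s0 = 1.5, ρ = 0.7, slope 1.05) and 47% (s1/s0 = 0.75, ρ = 0.3, slope 0.225).

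**Step 4: many zero doses.** A simulation with assumed use rates, 143 per arm and 2,000 trials per scenario, gave change-score CIs wider by 4.0% (ρ 0.82), 8.7% (0.65), 11.5% (0.53) and 21.7% (0.27). Coverage was 94% to 95% for both methods.

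**The case against.** The strongest reply is that nothing here is wrong. Randomization keeps the raw difference unbiased, simulated coverage is nominal, and Section 5.5 puts this endpoint on a complementary or exploratory footing. That stands, and it limits the point to precision.

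Second, the SAP never says the difference is unadjusted. The Summary marking in Section 7.3.1 does not settle it: the endpoint for a hemoglobin rise above 2.0 g/dL carries the same marking, yet Section 15.6.3 sends its odds ratio to the logistic model of Section 7.2.5. The table shells are in separate documents. This also stands, so the exact statement is that no method is named and unadjusted is the natural reading. The comparison cuts the other way too, because for that endpoint Section 15.6.3 names the model and for oral iron dose it names none.

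Third, baseline iron is not ignored, since doses are also tabulated by baseline iron use (Table 2.84). Those tables would show an imbalance in use, but they give no adjusted overall difference.

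Fourth, the size of the gain rests wholly on assumed values. That is so, and only the direction is free of them.

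**Conclusion.** The point holds as a no-cost improvement to an other-secondary endpoint. Its direction follows from the algebra in large samples. Its size depends on a correlation and an SD ratio that the SAP does not give: with equal SDs it is appreciable at low to moderate correlation, and small from about 0.75 upward.

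Stronger readings that a reader might draw are not supported:

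- **That the interval is invalid or biased.** It is neither.
- **That the power gain stays material until ρ nears 0.9.** Under equal SDs it is already below 5 points at about 0.75.
- **That the gain can be stated as extra subjects on the planned 286.** That figure is planned non-dialysis enrolment. ITT drops Cohort 1 ESA non-users (Section 4), and subjects withdrawn before Week 40 have no Quarter 4 value (Section 15.6.3).
- **That a change score over-corrects baseline imbalance whenever ρ is below 1.** That holds only with equal SDs. The criterion is the slope ρ·s1/s0, and if that exceeds 1 the change score under-corrects.

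**What to change.** In Section 7.3.2, or as an added entry in Section 7.3.5.1, specify for ITT, for each quarter and for the whole treatment period, an ANCOVA of monthly average oral iron dose on treatment and screening-period monthly oral iron dose, with robust standard errors because many doses will be zero. Report the adjusted difference (daprodustat minus epoetin beta pegol) and its 95% CI in Table 2.82 in place of the raw difference of change scores. The descriptive statistics for the change can stay. With baseline as a covariate, the estimated difference is the same whether dose or change is the outcome.

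The cost is a sentence or two of SAP text and five regressions (four quarters plus the whole period). No new data are needed. If adjustment was already intended, the same text simply records it.
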